6.1 Accrual and sample size calculations

Recruitment will target enrolling approximately 74 healthy, HIV-uninfected adult participants into five groups receiving IV administration of either VRC01 or VRC01LS at different schedules and/or dose levels. Groups 1 and 2 participants receive 4 infusions of VRC01 every 2 months at the 10 mg/Kg and 30 mg/Kg dose levels, respectively; Group 3 participants receive 3 infusions of VRC01LS every 3 months at the 30 mg/Kg dose level; Groups 4 and 5 participants receive a single infusion of VRC01 or VRC01LS, respectively, at the 30mg/Kg dose level. Because Groups 1-3 will be enrolled at different sites from Groups 4 and 5, Groups 1-3 were originally randomized with a ratio of 1:1:1, stratified by sex at birth and, separately, Groups 4 and 5 were also originally randomized with a ratio of 1:1 stratified by sex at birth. Groups 3 and 5 will stop enrolling once a minimal number of 12 participants, regardless of sex at birth, are enrolled. At that point, Groups 1 and 2 will be randomized together with a ratio of 1:1, stratified by sex at birth. Groups 1 and 2 will still be enrolled at different sites from Group 4. Groups 1 and 2 (n=23/group) will now be randomized with a ratio of 1:1, stratified by sex at birth. A total of 10 male and 13 female participants will still be enrolled in each of Groups 1 and 2. In Groups 1-3, enrollment is concurrent with the first biopsy procedure(s). In Groups 4-5, enrollment is concurrent with the first infusion. For all groups, randomization occurs prior to the first infusion, ideally within 4 days.

All participants receiving the first complete or partial infusion will provide some safety data. However, for PK analyses of drug levels in serum and mucosa, it is possible that data may be missing for various reasons, such as participants terminating from the study early, or problems in obtaining or shipping specimens. For this reason, the sample size calculations in Section 6.1.2 account for 15% enrolled participants having missing data for the primary lab data endpoint.

6.1.1 Sample size calculations for safety

The goal of the safety evaluation in this study is to identify safety concerns associated with product administration. The ability of the study to detect SAEs can be expressed by the true event rate above which at least 1 SAE would likely be observed and the true event rate below which no events would likely be observed. Specifically, for a group size of n=16, there is a 90% chance of observing at least 1 event if the true rate of such an event is 13.39% or more; and there is a 90% chance of observing no events if the true rate is 0.64% or less. For a group size of n=23, there is a 90% chance of observing at least 1 event if the true rate of such an event is 9.52% or more; and there is a 90% chance of observing no events if the true rate is 0.45% or less. For all three VRC01 groups combined (n=62), there is a 90% chance of observing at least 1 event if the true rate of such an event is 3.50% or more; and there is a 90% chance of observing no events if the true rate is 0.16% or less. For both VRC01 groups at the 30 mg/Kg dose level combined (n=39), there is a 90% chance of observing at least 1 event if

the true rate of such an event is 5.72 % or more; and there is a 90% chance of observing no events if the true rate is 0.26 % or less. As a reference, in HVTN vaccine trials from December 2000 through December 2012, about 4% of participants who received placebos experienced an SAE.

Probabilities of observing 0, 1 or more, and 2 or more events among single arms or combined arms of sizes 5, 7, 12, 16, 23, 39, and 62 are presented in [Table 6-1](#) for a range of possible true AE or SAE rates. These calculations provide a more complete picture of the sensitivity of this study design to identify potential safety problems with either VRC01 or VRC01LS (based on the minimal sample sizes).

Table 6-1 Probability of observing 0 events, 1 or more events, and 2 or more events, among arms of size 5, 7, 12, 16, 23, 39, and 62, for a range of true event rates

True event rate (%)	Group Size	0 Events	1+ Events	2+ Events
1	5	0.95	0.05	<0.01
	7	0.93	0.07	<0.01
	12	0.89	0.11	<0.01
	16	0.85	0.15	0.01
	23	0.79	0.21	0.02
	39	0.68	0.32	0.06
	62	0.54	0.46	0.13
4	5	0.82	0.18	0.01
	7	0.75	0.25	0.03
	12	0.61	0.39	0.08
	16	0.52	0.48	0.13
	23	0.39	0.61	0.23
	39	0.20	0.80	0.47
	62	0.08	0.92	0.71
10	5	0.59	0.41	0.08
	7	0.48	0.52	0.15
	12	0.28	0.72	0.34
	16	0.19	0.81	0.49
	23	0.09	0.91	0.68
	39	0.02	0.98	0.91
	62	<0.01	>0.99	0.99
20	5	0.33	0.67	0.26
	7	0.21	0.79	0.42
	12	0.07	0.93	0.73
	16	0.03	0.97	0.86
	23	<0.01	>0.99	0.96
	39	<0.01	>0.99	>0.99
	62	<0.01	>0.99	>0.99
30	5	0.17	0.83	0.47
	7	0.08	0.92	0.67

	12	0.01	0.99	0.91
	16	<0.01	>0.99	0.97
	23	<0.01	>0.99	>0.99
	39	<0.01	>0.99	>0.99
	62	<0.01	>0.99	>0.99

An alternative way of describing the statistical properties of the study design is in terms of the 95% confidence interval for the true rate of an adverse event based on the observed data. Table 6-2 shows the 2-sided 95% confidence intervals for the probability of an event based on a particular observed rate. Calculations are done using the score test method (64). If none of 16 participants in either of the single infusion groups experiences a safety event, the 95% 2-sided upper confidence bound for the true rate of such events in the population is 19.36%. If none of 23 participants in Groups 1, 2, or 3 experiences a safety event, the 95% 2-sided upper confidence bound for the true rate of such events is 14.31%. If none of the 39 participants in the Groups 2+4 experiences a safety event, the 95% 2-sided upper confidence bound for the true rate of such events is 8.97%. For the total 62 participants in the VRC01 groups, the 95% 2-sided upper confidence bound for this rate is 5.83%.

Table 6-2 Two-sided 95% confidence intervals based on observing a particular rate of safety endpoints for single or combined arms of size 5, 7, 12, 16, 23, 39, and 62

Observed event rate	Confidence interval (%)
0/5	(0.00, 0.43)
1/5	(0.04, 0.62)
2/5	(0.12, 0.77)
0/7	(0.00, 0.35)
1/7	(0.03, 0.51)
2/7	(0.08, 0.64)
0/12	(0.00, 0.24)
1/12	(0.01, 0.35)
2/12	(0.05, 0.45)
0/16	(0.00, 19.36)
1/16	(1.11, 28.33)
2/16	(3.50, 36.02)
0/23	(0.00, 14.31)
1/23	(0.77, 20.99)
2/23	(2.42, 26.80)
0/39	(0.00, 8.97)
1/39	(0.45, 13.18)
2/39	(1.42, 16.89)

0/62	(0.00, 5.83)
1/62	(0.29, 8.59)
2/62	(0.89, 11.02)

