Study products and routes of administration

- **VRC01:** human monoclonal antibody (mAb) VRC-HIVMAB060-00-AB in formulation buffer at pH 5.8 in sufficient normal saline (Sodium Chloride for Injection 0.9%, USP) to be administered intravenously (IV)
- **VRC01LS:** human monoclonal antibody (mAb) VRC-HIVMAB080-00-AB in formulation buffer at pH 5.8 in sufficient normal saline (Sodium Chloride for Injection 0.9%, USP) to be administered IV

Table 3-1 Schema

Group	Treatment	Infusion schedule (Months)					
		N	M0	M2	M3	M4	M6
Group 1	VRC01 10 mg/kg	23	IV Infusion	IV Infusion		IV Infusion	IV Infusion
Group 2	VRC01 30 mg/kg	23	IV Infusion	IV Infusion		IV Infusion	IV Infusion
Group 3	VRC01LS 30 mg/kg	~6*	IV Infusion		IV Infusion		IV Infusion
Group 4	VRC01 30 mg/kg	16	IV Infusion				
Group 5	VRC01LS 30 mg/kg	~6*	IV Infusion				

*Enrollment will stop in Groups 3 and 5 when ≥ 12 volunteers have been enrolled across *both* groups (see Section 6.1).

Participants

About 74 healthy, HIV-uninfected adult volunteers aged 18 to 50 years, regardless of sex or gender

Design

Multicenter, randomized, open-label trial

Duration per participant

As VRC01LS is designed to have a longer half-life than VRC01, participants who receive VRC01 will be followed for 6 months after the last product administration and participants who receive VRC01LS will be followed for 12 months after the last product administration. Specifically,

Groups 1, 2, and 5: 12 months of scheduled clinic visits

Group 3: 18 months of scheduled clinic visits

Group 4: 6 months of scheduled clinic visits

Estimated total study duration

40 months (includes enrollment and follow-up)

Investigational New Drug (IND) sponsor

DAIDS, NIAID, NIH, DHHS (Bethesda, Maryland, USA)

Study products provider

Dale and Betty Bumpers Vaccine Research Center (VRC), NIAID, NIH, DHHS (Bethesda, Maryland, USA)

Core operations

HVTN Vaccine Leadership Group/Core Operations Center, Fred Hutchinson Cancer Research Center (FHCRC) (Seattle, Washington, USA)

Statistical and data management center (SDMC)

Statistical Center for HIV/AIDS Research and Prevention (SCHARP), FHCRC (Seattle, Washington, USA)

DF/Net Research (Seattle, Washington, USA)

HVTN Laboratory Center (LC)

• HIV diagnostic laboratories

- University of Washington Virology Specialty Laboratory (UW-VSL) (Seattle, Washington, USA)
- HIV Sero-Molecular Laboratory, National Institute for Communicable Diseases (HSML-NICD) (Johannesburg, South Africa)

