## 6. RANDOMIZATION

The randomization sequence will be obtained by computer-generated random numbers and provided to each HVTN CRS through the SDMC via a Web-based randomization system. Participants will be randomized to either one of Groups 1-3 or one of Groups 4-5, depending on site. The randomization will be stratified by sex at birth and done in blocks to ensure balance across Groups 1-3, and across Groups 4 and 5. All participants will be randomized prior to the first infusion, ideally within 4 days. At each institution, the pharmacist with primary responsibility for dispensing study products is charged with maintaining consistency of the treatment assignments.

After the trial started, the enrollment was capped in Groups 3 and 5 at  $n=7$  and  $n=10$ , respectively in November 2017 and December 2017, to limit the number of VRC01LS participants due to the emerging of other more superior mAb products in the field.

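### Section 6.1.1 gives the VRC01LS groups (3 and 5) zero-event safety bounds for n=23 and n=16, sizes they do not have, and nine Table 6-2 rows are proportions under a percent heading

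*Protocol*

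**What the plan says.** Protocol Section 6.1.1 describes safety precision by score-method 95% intervals. Two sentences of the text bear on VRC01LS:

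- "If none of 23 participants in Groups 1, 2, or 3 experiences a safety event", the upper bound is 14.31%. Group 3 receives VRC01LS.
- "If none of 16 participants in either of the single infusion groups experiences a safety event", the upper bound is 19.36%. Section 6.1 defines the single-infusion groups as Group 4 (VRC01) and Group 5 (VRC01LS).

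On group size, Section 6.1 says "Groups 3 and 5 will stop enrolling once a minimal number of 12 participants, regardless of sex at birth, are enrolled", and gives 23 per group to Groups 1 and 2 only. Table 3-1 in Section 3 lists about 6 for each of Groups 3 and 5 and 16 for Group 4, with a footnote stopping enrolment at 12 or more across Groups 3 and 5. SAP Section 6 records the outcome: "After the trial started, the enrollment was capped in Groups 3 and 5 at" 7 and 10 respectively.

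Section 6.1.1 also says that its tabulated calculations address "either VRC01 or VRC01LS (based on the minimal sample sizes"), and Tables 6-1 and 6-2 carry rows for n=5, 7 and 12. The interval column of Table 6-2 is headed in percent. Its 0/16 row reads (0.00, 19.36), while its 0/12 row reads (0.00, 0.24).

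For the three VRC01 groups combined (n=62), the section gives a 90% chance of seeing at least one event if "the true rate of such an event is 3.50% or more".

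**The concern.** Primary objective 1 covers the safety of both antibodies. VRC01LS has much the smaller prior human exposure in the protocol's background: 39 recipients as of July 2017 (Section 4.7.2), against more than 2600 HIV-uninfected adults given VRC01 as of February 2018 (Section 4.7.1). A reader who takes the two sentences at face value would conclude that a clean Group 3 rules out event rates above about 14%, and a clean Group 5 rates above about 19%. Neither group is large enough for that.

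The table does not repair the text. Its small-n rows are the only intervals in the section at VRC01LS sizes, and they are in the wrong unit for their heading. No correctly labelled interval for the VRC01LS arms therefore appears in the section.

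**Working it through.** **Inputs.** Two-sided 95% score intervals (Section 6.1.1), so z² = 1.96² = 3.8415. Group sizes come from Table 3-1, Section 6.1 and SAP Section 6.

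**1. Reproduce the plan's figures.** With zero events the score (Wilson) upper limit is z²/(n + z²).

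| n | Calculation | Result | Protocol |
|---|---|---|---|
| 16 | 3.8415/19.8415 | 19.36% | 19.36% |
| 23 | 3.8415/26.8415 | 14.31% | 14.31% |
| 39 | 3.8415/42.8415 | 8.97% | 8.97% |
| 62 | 3.8415/65.8415 | 5.83% | 5.83% |

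All twelve Table 6-2 rows for these sizes reproduce to two decimals. Clopper-Pearson (20.59% for 0/16) and Agresti-Coull (22.69%) do not match, so the method is not in doubt.

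**2. The same formula at VRC01LS sizes.**

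| Arm | n | Calculation | Upper bound | Stated in text |
|---|---|---|---|---|
| Group 3 or 5, planned | about 6 | 3.8415/9.8415 | 39.03% | 14.31% (Group 3), 19.36% (Group 5) |
| Group 3, SAP | 7 | 3.8415/10.8415 | 35.43% | 14.31% |
| Group 5, SAP | 10 | 3.8415/13.8415 | 27.75% | 19.36% |
| Combined, minimum | 12 | 3.8415/15.8415 | 24.25% | none |
| Combined, SAP | 17 | 3.8415/20.8415 | 18.43% | none |

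At n=6 the bound is 39.03/14.31 = 2.7 times the Group 3 figure and 39.03/19.36 = 2.0 times the Group 5 figure. At the SAP sizes the ratios are 2.5 and 1.4.

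**3. What zero events would mean.** P(no events) = (1 − p)ⁿ.

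- p = 0.1431: 0.8569⁶ = 0.396 and 0.8569⁷ = 0.339, against 0.8569²³ = 0.029.
- p = 0.1936: 0.8064⁶ = 0.275 and 0.8064¹⁰ = 0.116, against 0.8064¹⁶ = 0.032.

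**4. Table 6-2 units.** The score intervals in percent, beside the printed values:

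| Row | Printed | In percent |
|---|---|---|
| 0/5 | 0.00, 0.43 | 0.00, 43.45 |
| 1/5 | 0.04, 0.62 | 3.62, 62.45 |
| 2/5 | 0.12, 0.77 | 11.76, 76.93 |
| 0/7 | 0.00, 0.35 | 0.00, 35.43 |
| 1/7 | 0.03, 0.51 | 2.57, 51.31 |
| 2/7 | 0.08, 0.64 | 8.22, 64.11 |
| 0/12 | 0.00, 0.24 | 0.00, 24.25 |
| 1/12 | 0.01, 0.35 | 1.49, 35.39 |
| 2/12 | 0.05, 0.45 | 4.70, 44.80 |

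Every printed value equals the correct limit divided by 100 and rounded.

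**5. Detection rate at n=62.** The rate giving a 90% chance of at least one event is 1 − 0.1^(1/n). At n=62 this is 3.65%, against 3.50% stated; at 3.50% the chance is 1 − 0.965⁶² = 0.890. The formula gives 13.40%, 9.53% and 5.73% at n=16, 23 and 39, against 13.39%, 9.52% and 5.72% stated, so rounding does not explain the n=62 figure.

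**The case against.** The case for treating this as purely editorial has several parts.

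- **Nothing depends on the figures.** Adverse events are not formally compared between arms, pause rules are triggered by individual events, and the SAP does not reuse these bounds. This stands in full, and it limits how much the point matters.
- **The section already shows the small sizes.** Table 6-1 is correct at n=5, 7 and 12 and makes the low sensitivity plain. This also stands: the limit is contradicted in the text, not hidden.
- **The sentences are conditional, and true for 23 or 16 participants.** A reader who has seen Table 3-1 should notice the mismatch. But the sentences name groups that cannot meet the condition, so the conditional form does not make them right for Groups 3 and 5.
- **The unit slip is obvious.** Read as percentages, the 1/5 interval would exclude the observed 20%. Agreed; it is a slip, and the values are right as proportions.
- **Neither table has n=6, and that size is only approximate.** True, but about 6 is the protocol's own planned size for each group, and a bound in the text needs no table row.
- **The n=62 item is small, and other rates there are slightly off.** It is small. The no-event rates at n=16 and n=62 (0.64% and 0.16% stated, 0.66% and 0.17% computed) remain true as worded, because the stated rates are the lower ones. The 3.50% statement does not, since the chance at that rate is below 90%.

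**Conclusion.** The concern holds. Two sentences attribute to Groups 3 and 5 a zero-event precision that those groups cannot deliver. The stated bounds of 14.31% and 19.36% should both be about 39.0% at the planned size, or 35.4% and 27.8% at the SAP sizes. Nine rows of Table 6-2 need conversion to percent, and one detection rate is low by 0.15 percentage points. The bounds for Groups 1, 2 and 4 and for the combined VRC01 groups are correct, as is Table 6-1.

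The version history notes an amendment changing the sizes of Groups 3 and 5. The likely explanation is that the tables were extended for it and the two sentences were not; this is an inference.

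The conclusion rests on the score method, which the protocol names and which reproduces its other bounds, and on reading the approximate size in Table 3-1 as 6. It should be corrected because it misstates precision on a primary objective, but it does not affect the design or the analysis.

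**What to change.** In protocol Section 6.1.1:

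1. Restrict the n=23 sentence to Groups 1 and 2, and the n=16 sentence to Group 4.
2. Add one sentence with the VRC01LS zero-event upper bounds at planned sizes: 39.0% for about 6 per group and 24.2% for 12 combined. If enrolled sizes are shown too, label them as SAP sizes: 35.4% (n=7), 27.8% (n=10) and 18.4% (n=17).
3. Replace the nine Table 6-2 rows for n=5, 7 and 12 with the percent values tabulated above. Leave the group sizes in both tables unchanged.
4. Change 3.50% to 3.65% for n=62.

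The cost is two edited sentences, one new sentence, nine converted rows and one number. Design and analysis are untouched. The stated VRC01LS precision becomes less favourable.

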6.1.2 Sample size calculations for drug levels

The main goal of this study regarding drug levels involves a preliminary assessment of the correlation between serum and mucosa drug level measurements or corresponding PK parameters estimated after the administration of VRC01 or VRC01LS. The statistical power to detect different levels of correlation (ρ) can be calculated using the Z-transformation (ie, $Z' = \text{arctanh}(\rho) + \rho / (2 * (n-1))$) followed by normal approximation. As shown in [Table 6-3](#), there is limited power ($\leq 77\%$) to detect a correlation of 0.9 or lower in a group size of $n=6$ or lower. However, for Groups 2+4 (VRC01 30mg/Kg) with $n=15$ in the assessment of male mucosal compartment, there is approximately 87% power to detect a correlation of 0.7 or higher, and with $n = 17$ in the assessment of female mucosal compartment, there is approximately 91% power to detect a correlation of 0.7 or higher. For Groups 1+2+4 (VRC01 10mg/Kg or 30 mg/Kg) in the assessment of each mucosal compartment with $n=23$ in male or $n=25$ in female, there is $>88\%$ or $>94\%$ power, respectively, to detect a correlation of 0.6 or higher.

Based on earlier data in non-human primate studies with a total of 12 animals, the observed correlation between log-transformed peak serum and peak mucosa drug levels after a single infusion of VRC01 is in the range of 0.6 to 0.9 (personal communications with VRC colleagues). Therefore, this study is expected to provide reasonable power to achieve the primary objectives regarding drug levels for the combined VRC01 groups if the true correlation between serum and mucosa drug levels is similar to what was observed in the animal studies. There may be a reasonable power ($> 77\%$) to detect correlations between serum and mucosal drug levels in the VRC01LS groups if such data are available from at least 6 participants and the true correlation is at least 0.9.

Table 6-3 Statistical power (%) to detect different levels of correlation between log-transformed serum and mucosal drug levels in group sizes of 6-28 assuming 15% missing data, respectively, in Group 4, Group 1 or 2, Groups 2+4, and Groups 1+2+4 for each

mucosal compartment among males or females (assuming 10 males and 13 females in groups 1 and 2, and 8 males and 8 females in group 4).

True correlation coefficient	Sample size for each mucosal compartment						
	6	8	11	15	17	23	28
0.3	9	11	15	20	22	29	35
0.4	13	17	24	33	37	49	58
0.5	18	25	37	50	56	71	80
0.6	26	37	53	69	76	88	94
0.7	37	53	72	87	91	98	99
0.8	53	73	89	97	99	100	100
0.9	77	93	99	100	100	100	100

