Initial analyses were generated including VRC01 serum levels up to the day 168 visit. The trough level in Group 1 reached an average of 75.6 (64.6, 88.5) ug/ml before the second infusion (day 28), then decreased to trough levels of 50.7 (43, 59.8), 43.4 (36.8, 51.2), 37.3 (26.7, 52.1), and 31.7 (19.9, 50.3), prior to the 3rd (day 56), 4th (day 84), 5th (day 112), and 6th (day 140) infusions, respectively. The last measured level, 28 days after the 6th infusion, was 39.7 (28, 56.3) ug/ml. In Group 2, the trough levels, measured before the second (day 56) and third (day 112) infusions, averaged 20.1 (16.4, 24.6) ug/ml and 21.4 (15.7, 29.2) ug/ml, respectively. The last trough level observation, 28 days after the 3rd infusion, measured 15.1 (6.5, 35.3) ug/ml. In Group 3 (including placebo recipients), the trough levels, measured right before each subsequent 2-weekly SC injection, decreased steadily from 27.7 (8.8, 87.7) ug/ml at day 28 to 8.2 (2.6, 26.3) ug/ml at day 154. The last trough measurement at 14 days after the SC injection was 6 (1.9, 19.3) ug/ml. In Group 4, the trough levels, measured before the second (day 56) and third (day 112) infusions, averaged 4.1 (3.1, 5.3) ug/ml and 2.5 (0.8, 7.9) ug/ml, respectively. The last trough level observation, 28 days after the 3rd infusion, measured 4.2 (1.6, 11.4) ug/ml. In Group 5, the trough levels, measured before the second (day 56) and third (day 112) infusions, averaged 10.4 (6.8, 16.1) ug/ml and 11.5 (7.5, 17.5) ug/ml, respectively. The last trough level observation, 28 days after the 3rd infusion, measured 11.9 (3.8, 38) ug/ml. VRC01 serum levels for Group 4 and Group 5, which use the same doses as HVTN 116, ie VRC01 10mg/kg and 30mg/kg at two month intervals respectively, are shown in [Figure 4-6](#) and [Figure 4-7](#).

[figure not shown]

Figure 4-6 VRC01 serum levels in the HVTN 104 per-protocol analysis for Group 4.

[figure not shown]

Figure 4-7 VRC01 serum levels in the HVTN 104 per-protocol analysis for Group 5.

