be utilized to incorporate outcome responses over several timepoints and to account for subject heterogeneity. MAR assumes that the probability of an observation being missing may depend upon the observed responses and upon observed covariates, but not upon any unobserved factors. Generalized nonlinear models for response rates will use a binomial error distribution and for quantitative endpoints, a normal error distribution. All models will include as covariates all available baseline predictors of the missing outcomes.

In addition, non-compartment PK analysis will be performed to estimate PK parameters from individual time-concentration curves. The correlation between individual-level PK parameters estimated for different specimen types (serum vs. mucosa) may also be assessed. All statistical tests will be 2-sided and will be considered statistically significant if $p \leq 0.05$.

For the analysis of correlation between two continuous assay variables over time, graphical summary and tabular summary of the sample correlation at each given timepoint will be made. Cross-correlation of the 2 variables with different time lags may also be calculated and visually displayed if there are at least 10 participants with no missing data over time from both variables. Nonlinear or linear mixed effects models may also be used to predict mucosal drug levels based on serum drug levels collected at the same or previous timepoints. More details of the statistical analysis approaches will be described in a separate Statistical Analysis Plan document.

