More sophisticated analyses of drug-level data and other assay data collected over time employing repeated measures methodology that is valid under the missing at random (MAR) assumption (for example, nonlinear mixed effects models) may be utilized to incorporate outcome responses over several timepoints and to account for subject heterogeneity. MAR assumes that the probability of an observation being missing may depend upon the observed responses and upon observed covariates, but not upon any unobserved data. Generalized nonlinear models for response rates will use a binomial error distribution and for quantitative endpoints, a normal error distribution. All models will include as covariates all available baseline predictors of the missing outcomes.

In addition, non-compartment PK analysis will be performed to estimate PK parameters from individual time-concentration curves. The correlation between individual-level PK parameters estimated for different specimen types (serum vs. mucosa) may also be assessed. All statistical tests will be 2-sided and will be considered statistically significant if  $p \leq 0.05$ .

For the analysis of correlation between two continuous assay variables over time, graphical summary and tabular summary of the sample correlation at each given timepoint will be made. Cross-correlation of the 2 variables with different time lags may also be calculated and visually displayed if there are at least 10 participants with no missing data over time from both variables. Nonlinear or linear mixed effects models may also be used to predict mucosal drug levels based on serum drug levels collected at the same or previous timepoints.

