### 10.2.2. List of Graphs

- Boxplots of baseline mucosal level normalized by total IgG, by sex at birth, tissue type, and treatment arm
- Boxplots of baseline mucosal level normalized by protein, by sex at birth, tissue type, and treatment arm
- Boxplots of baseline mucosal level without normalization, by sex at birth, tissue type, and treatment arm
- Lineplots of baseline and post-infusion mucosal level normalized by total IgG, by sex at birth, tissue type, and treatment arm
- Lineplots of baseline and post-infusion mucosal level normalized by protein, by sex at birth, tissue type, and treatment arm
- Lineplots of baseline and post-infusion mucosal level without normalization, by sex at birth, tissue type, and treatment arm

- Scatterplots of correlation as following:

Cervicovaginal secretions to Cervical homogenates

Cervicovaginal secretions to Vaginal homogenates

Blood to Cervical homogenates

Blood to Vaginal homogenates

Blood to Cervicovaginal secretions

Rectal secretions to rectal homogenates

Rectal secretions to Semen

Rectal secretions to blood

Rectal homogenates to Semen

Rectal homogenates to blood

Rectal homogenates to Cervical lysates

Rectal homogenates to vaginal lysates

Rectal homogenates to cervicovaginal secretions

Rectal secretion to Cervical lysates

Rectal secretion to vaginal lysates

Rectal secretion to cervicovaginal secretions

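### The power claim at a serum–mucosa correlation of 0.6 rests on pooling 10 and 30 mg/kg with no dose or group term; if levels are correlated that way, dose alone can make the result significant

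*Protocol*

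**What the plan says.** Protocol section 6.1.2 makes a preliminary assessment of the correlation between serum and mucosal drug levels, or the matching PK parameters, the main drug-level goal. Power uses the Fisher transformation, "Z' = \text{arctanh}(\rho) + \rho / (2 * (n-1))$) followed by normal approximation", which has no term for dose or group.

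The text gives power for Groups 2+4 (30 mg/kg only) at a correlation of 0.7, and at 0.6 for the set pooled over both doses: "For Groups 1+2+4 (VRC01 10mg/Kg or 30 mg/Kg) in the assessment of each mucosal compartment". It concludes that "this study is expected to provide reasonable power to achieve the primary objectives regarding drug levels for the combined VRC01 groups". The planning range, from non-human primates, is 0.6 to 0.9.

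For the analysis, SAP section 8.5.1 promises a scatterplot matrix with correlation coefficients, and says that "graphical summary and tabular summary of the sample correlation at each given timepoint will be made". Mixed models predicting mucosal from serum levels are optional, and no covariate for dose is named. The scatterplot list in SAP section 10.2.2 runs by specimen pair, for example "Blood to Cervical homogenates", with no arm qualifier. The significance rule is general: "All statistical tests will be 2-sided and will be considered statistically significant if $p \leq 0.05".

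The SAP does stratify elsewhere. Section 8.5.2 stratifies the infectivity comparisons between tissues by dose group, section 10.1.2 splits the infectivity scatterplots by treatment arm, and section 10.2.2 splits the mucosal boxplots and lineplots by treatment arm.

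**The concern.** Dose raises serum and mucosal levels together. A scatter that mixes 10 and 30 mg/kg participants is therefore two clusters, one shifted up and to the right of the other. Its overall correlation is positive even if, among people given the same dose, serum says nothing about mucosa.

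The trial is meant to bridge serum levels to mucosal levels for the efficacy trials (protocol section 4.4). For that use, what matters is whether a person with higher serum than others on the same dose also has higher mucosal levels. A pooled rejection of zero need not answer that question, because it can arise only from more drug having been given.

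This is separate from visit timing. Secretions at Visits 4 and 5 are collected in Groups 1, 2 and 4 at the same time after one infusion, so at those visits only the dose differs by design.

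**Working it through.** **1. Reproduce the stated power.** Power = Φ(Z′·√(n−3) − 1.96), with Z′ = arctanh(0.6) + 0.6/(2(n−1)) and arctanh(0.6) = 0.6931.

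- n=23: Z′ = 0.7068; 0.7068 × √20 − 1.96 = 1.20; power 88.5%.
- n=28: Z′ = 0.7043; 0.7043 × √25 − 1.96 = 1.56; power 94.1%.
- n=25: Z′ = 0.7056; 0.7056 × √22 − 1.96 = 1.35; power 91.1%.

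The stated figures are arithmetically right, but the 94% belongs to n=28. The text reads "mucosal compartment with $n=23$ in male or $n=25$ in female", while Table 6-3 has a column for 28 and none for 25. The allocation gives 0.85 × (13+13+8) = 28.9 for women and 0.85 × (10+10+8) = 23.8 for men. For Groups 2+4 (n=15 and 17), Table 6-3 gives 69% and 76% at 0.6, and 87% and 91% at 0.7.

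**2. Inputs for the pooled correlation.**

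- Evaluable participants at 10 and 30 mg/kg: men 8 and 15, women 11 and 17.
- Log dose shift D: ln 3 = 1.10 if levels are dose-proportional, or ln(10.4/4.1) = 0.93 from the HVTN 104 day-56 troughs (protocol section 4.7.1.3). The 30 mg/kg troughs there "averaged 10.4 (6.8, 16.1) ug/ml and 11.5 (7.5, 17.5) ug/ml, respectively"; the 10 mg/kg day-56 figure is 4.1 (3.1, 5.3).
- Serum log SD, reading those intervals as 95% CIs with n=12 (Table 4-10): ln(5.3/3.1)/(2 × 2.201) × √12 = 0.42 at 10 mg/kg; ln(16.1/6.8)/(2 × 2.201) × √12 = 0.68 at 30 mg/kg.
- Mucosal log SD: not in the documents. Assumed range 0.5 to 2.0.
- Mucosal levels shift with dose by the same D. Within-dose correlation is set to zero.

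**3. Induced correlation.** r = B / √[(B + s_s²)(B + s_m²)]. Here B = p(1−p)D², p is the 10 mg/kg share, s_s² is the average within-dose serum variance and s_m is the mucosal SD.

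Men, D = 1.10:
- p = 8/23 = 0.348, so B = 0.348 × 0.652 × 1.21 = 0.274.
- s_s² = 0.348 × 0.42² + 0.652 × 0.68² = 0.363.
- With s_m = 0.5, r = 0.274/√(0.637 × 0.524) = 0.47. With s_m = 1.0, r = 0.30.

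The pooled Fisher test rejects when |r| exceeds tanh(1.96/√20) = 0.41 (n=23) or tanh(1.96/√25) = 0.37 (n=28).

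**4. How often the pooled test rejects** (simulated trials, zero within-dose correlation; each cell gives D = 0.93, then D = 1.10):

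| Mucosal log SD | Men (8+15) | Women (11+17) |
|---|---|---|
| 0.5 | 51%, 72% | 65%, 85% |
| 1.0 | 20%, 31% | 27%, 41% |
| 2.0 | 9%, 12% | 11%, 15% |

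A partial correlation adjusted for dose or for treatment group rejects about 5% in every cell.

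**5. Power after adjustment for treatment group.** Three groups use two further degrees of freedom, so the SE is 1/√(n−5). At a within-group correlation of 0.6:

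- n=23: 0.7068 × √18 − 1.96 = 1.04; about 85%.
- n=28: 0.7043 × √23 − 1.96 = 1.42; about 92%.
- n=25: 0.7056 × √20 − 1.96 = 1.20; about 88%.

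**The case against.** Several points against the concern have force.

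- **The SAP does not prescribe a pooled test.** A reader might infer from section 6.1.2 that the trial will test a correlation pooled over doses. The documents do not say so. Pooling appears in the power text; the SAP is silent on whether correlations are by arm, by dose or pooled, and its table and graph lists contain no correlation p-value. The rates above apply only if the analysis follows the power case. What stands is that nothing in the plan prevents this, and the claim at 0.6 depends on it.
- **The pooled set is not the only powered set.** Groups 2+4, at one dose, reach 87% and 91% at 0.7, inside the planning range. So it would be wrong to say that the drug-level objective as a whole rests on mixing doses. Only adequate power at 0.6 does.
- **The pooled correlation is a genuine marginal association.** The efficacy trials use both doses, so association across that exposure range is relevant. It is a different quantity from within-dose tracking and should be labelled as such.
- **PK parameters may escape the problem.** Half-life and terminal rate do not scale with dose under linear kinetics. The point is limited to correlations of levels.
- **The size is uncertain.** A reader might infer that a false positive is close to certain. That needs a small mucosal SD and a serum SD below both HVTN 104 values. SAP section 8.5.2 says that dilution from sample collection and processing cannot be determined, which could add mucosal variance. The HVTN 104 inputs are also day-56 troughs, not Visit 4 or 5 levels.

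The plan also calls the assessment preliminary and admits that small groups limit inference. That tempers the consequences but does not remove the ambiguity.

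**Conclusion.** The concern holds in a limited form. Adequate power at 0.6 is claimed only for a set that mixes 10 and 30 mg/kg without a dose or group term, and the SAP's level correlations name no adjustment. If they are pooled that way, rejection with zero within-dose correlation exceeds the nominal 5% in every setting examined. The full range is about 9–72% for men and 11–85% for women, driven mainly by the mucosal SD.

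These rates assume equal dose shifts in serum and mucosa and HVTN 104 intervals that are 95% CIs. They are not a forecast of the trial's error rate. The stated power is correctly calculated; the problem is what a pooled correlation would show. The direction is secure, the size is not.

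**What to change.** - For any level correlation pooled over Groups 1, 2 and 4, make the partial correlation adjusted for treatment group the main estimate: correlate the residuals of log serum and log mucosa after removing group means, with Fisher SE 1/√(n−5).
- Adjust for group rather than dose alone. Groups 2 and 4 share a dose but differ in number of infusions and in sites. Their only shared post-infusion biopsy visit, Visit 14, falls 1–15 days after the fourth infusion in Groups 1 and 2, but about six months after the single infusion in Group 4.
- Show the within-dose correlations beside it and mark the treatment arm in the section 10.2.2 scatterplots. If an unadjusted pooled value is also reported, label it as marginal.
- Restate the section 6.1.2 power at 0.6 as about 85% for men (n=23) and 92% for women (n=28), and reconcile the text's n=25 for women with Table 6-3. If 25 is right, the adjusted power is about 88%.

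The cost is SAP and protocol wording plus 2 to 3 points of stated power on the rounded figures (88% to 85%, 94% to 92%). No new data are needed.
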